4.17.1 Adverse Events/Serious Adverse Events

Adverse events will be coded using MedDRA latest available version.

All reported AEs will be listed along with the date of onset, date of resolution (if AE is resolved), investigator's assessment of intensity, outcome, action taken with IP, and possible relationship to study drug (assessed by investigator). A by subject listing of all AE (including AEs before first dose of study medication) will be provided. This listing will include the following information: study period, verbatim term, MedDRA SOC, and preferred term, start date/time, end date/time, time from last dose, intensity, causality, action taken, whether the AE was classified as serious, the outcome of the AE and the concomitant or additional treatment given, if any. Any AE occurring before the first dose of IP and/or the AE assessments that are unresolved at the participant's last assessment in the study will be included in the data listings but will not be included in the summary tables of AEs.

Multiple occurrences of an AE in the same subject will only be counted once overall considering start date as the first day of first occurrence and stop date the last day of the last occurrence and the AE will assigned to the treatment of the first occurrence period study drug. Multiple occurrences of an AE in the same subject for the same treatment will only be counted once for that treatment.

Statistical Analysis Plan

The number of subjects will be tabulated also by SOC, preferred term, and treatment.

In the case that, during the study, a subject has more than 1 episode of the same preferred term with different levels of intensity, action taken, outcome causality or seriousness, then the maximum intensity level, action taken (ie, withdrawn) and outcome (ie, fatal), causality level (ie, related), or seriousness level (ie, serious), respectively will be used.

The following ordering will be used to define maximum intensity level, action taken, outcome causality level, or seriousness level:

- Intensity: Mild < Moderate < Severe
- Causality: No < Yes
- Seriousness: No < Yes
- Action taken: Unknown < Not applicable < Dose not changed < Drug interrupted < Drug withdrawn
- Outcome: Unknown < Recovered/resolved < Recovered/resolved with sequelae < Recovering/ resolving < Not recovered/not resolved < Fatal

A general summary of all AEs will show the number and percentage of subjects with:

- Any AE
- Any SAE
- Any SAE with outcome death

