- SOC and preferred term.
- SOC, preferred term, and maximum intensity.
- SOC, preferred term, and relationship to study intervention judged by investigator.

Adverse event summaries will be ordered in terms of decreasing frequency for SOC, and preferred term within SOC.

The tables of AE will include all the AEs with an onset date and time on or after the date and time of first dose of IP up to the end of treatment + 96 hours. Additional tables including all the AEs experienced after the IP until last follow-up (Day 56) and for ADA status will be reported for both Part 1 and Part 2.

Adverse events sorted by decreasing frequency and AEs leading to discontinuation of investigational product by SOC and preferred term will be summarised.

The number and percentage of subjects who experience 1 or more SAEs will be tabulated by treatment group (AZD1402 and placebo) and by SOC and preferred term and by SOC and preferred term and with outcome of death.

For each subject and each AE, the worst severity recorded will be attributed and used in the by-severity summaries. Similarly, the worst causality (most related to treatment) will be attributed and used in the by-causality summaries. If severity or causality is missing, a conservative approach for AE assessment (taking into account the worst case) will be followed.

Key subject information for participants experiencing SAE with outcome death, SAEs, and AEs leading to discontinuation of IP will be presented in a listing. All the AE will be included in the data listings.

Statistical Analysis Plan

For AEs with partial dates/times, worst case is always assumed; if possibly on-treatment, then on-treatment is assumed, on-treatment AEs will be considered to have the longest possible duration and off-treatment AEs will be considered to have the shortest possible duration. In accordance with this principle, any AEs with incomplete start and end dates/times will be treated as follows:

- AEs with unknown start times, but with start date known, will be imputed with a time of 00:00, unless the start date corresponds to any given dosing date. In this case the start time will be imputed with the time of dosing. If this results in a start date/time after end date/time of the AE, then the time will also be imputed with 00:00.

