- AEs with completely unknown start dates will be imputed with the date and time of dosing, unless the end date is known and prior to dosing; in that case the start date will be imputed as the date of Screening and a time of 00:00.
- AEs with partially known start dates/times will be treated as follows:
 - If only the day is missing, then the day will be imputed with the first day of the month, unless the month and year in which the AE started is a month and year in which IP was administered, then the day will be imputed with the first day on which IP was administered in that month. If this results in a start date after the end date, then the day will be imputed with the first day of the month.
 - If only the month is missing and the year is a year in which IP was administered, then the month will be imputed with the first month in which IP was administered. If this results in a start date after the end date of the AE, then the month will be imputed with JAN. If the known year part is not a year in which IP was administered, then the month will also be imputed with JAN.
 - If both the day and month is missing and the year is a year in which IP was administered, then the day and month will be imputed with the day and month of dosing. If this results in a start date after end date, then the day and month will be imputed with 01JAN. If the year is not a year in which IP was administered, then the day and month will also be imputed with 01JAN.
 - If only the year is missing, then the year will be imputed with the year of dosing.

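### When only the month of an AE start date is missing, the SAP's rule can date a possibly on-treatment event before first dose and drop it from the AE tables, against its own worst-case principle

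*SAP*

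**What the plan says.** SAP section 4.17.1 states the principle first: "For AEs with partial dates/times, worst case is always assumed; if possibly on-treatment, then on-treatment is assumed". The detailed rules for incomplete dates are presented as following from it.

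Where only the month is missing and the year is one in which study drug was given, "then the month will be imputed with the first month in which IP was administered". One correction is attached: "If this results in a start date after the end date of the AE, then the month will be imputed with JAN".

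The same section defines what reaches the tables. The main AE tables take events with onset "on or after the date and time of first dose of IP up to the end of treatment + 96 hours". The additional tables, which run to the last follow-up, also start only after study drug. On the other side of first dose, "Any AE occurring before the first dose of IP" goes to the listings only: such events "will be included in the data listings but will not be included in the summary tables of AEs".

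**The concern.** The month-only rule keeps the recorded day and tests the result only against the AE end date. It never asks whether the result is on or after first dose, and its one fallback, January, usually moves the date earlier still. Treatment lasts 28 days (protocol synopsis), so dosing usually spans two calendar months. If the true onset is in the second month and its day number is lower than the first-dose day, the rule puts the event before dosing.

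The neighbouring rules do not share this gap. A missing day is tied to the first dosing day in that month. A missing day and month take the day and month of dosing. A wholly unknown start takes the dosing date. Each defaults to dosing unless its end-date exception applies. So an AE with both day and month missing is counted, while one with the day known can be left out.

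Safety is the primary objective of Part 1, where each active dose has about 10 participants (30 randomised 1:1:1 in Part 1a; 15 randomised 2:1 in Part 1b). If the omitted event were a participant's only one in its category, that incidence would move by 1/10, or 10 percentage points.

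**Working it through.** The plan gives no figure to reproduce, so the check applies the rule as written.

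**Inputs.** 28-day treatment period (protocol synopsis); table window ending 96 hours after end of treatment, so 28 + 4 = 32 days (SAP 4.17.1); the month-only rule with its January fallback (SAP 4.17.1). Assumptions: a 365-day year (2022), all first-dose dates and onset days equally likely, and an AE end date two days after onset. If dosing crosses New Year, the first dosing month is the first one in the AE's recorded year.

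**Worked example.** First dose 20 March 2023, last dose 16 April. The AE start is recorded as day 05, month unknown, 2023; its end date is 8 April.
- 5 April is possible and on treatment: 12 days in March (20th to 31st) + 5 = study Day 17.
- The rule gives 5 March, 20 − 5 = 15 days before first dose.
- 5 March is not after 8 April, so the fallback does not apply and the event is not tabulated.

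**Count per first-dose date, 28-day period.** For first dose on day d of a month with L days, L − d + 1 treatment days fall in that month. The other 28 − (L − d + 1) = d + 27 − L fall in the next, when this is positive. Their day numbers are all below d, so all are dated before first dose. For L = 30 this is d − 3:

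| First dose on day | On-treatment days misdated, of 28 |
|---|---|
| 1 to 3 | 0 |
| 10 | 7 |
| 20 | 17 |
| 30 | 27 |

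**Whole year, 28-day period.** Whatever the month length, the counts run 1, 2, …, 27 over the last 27 start days, so each month contributes 27 × 28 / 2 = 378. December starts contribute none, because an onset in the next year is put in January, which is correct. Total: 11 × 378 = 4,158 of 365 × 28 = 10,220, or 40.7%. At least one day is misdated for 11 × 27 = 297 of the 365 start dates.

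**Whole year, 32-day window.** Direct enumeration gives 4,915 of 365 × 32 = 11,680, or 42.1%, with 323 of 365 start dates affected. Ten further combinations produce a date that does not exist, such as day 31 in a 30-day month. The SAP has no instruction for these.

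**After the change.** Choosing the earliest month that puts the date inside the window and not after the AE end date leaves 0 of 10,220 and 0 of 11,680 truly on-treatment combinations before first dose.

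**The case against.** The strongest reply is that the case hardly arises. AE start dates and times are collected. Part 2 participants are seen about weekly during treatment, and Part 1 participants are resident for at least two weeks. A site that knows the onset was on the 5th but not in which month is hard to picture. This stands: the documents support no expected count, and no table or conclusion can be shown to change.

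A reader might infer that on-treatment events vanish from the report. They do not. All AEs are listed, and SAEs, deaths and AEs leading to discontinuation also have a listing of key participant information.

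A reader might also infer that the rule demonstrably misclassifies events. The documents do not support that either. SAP 3.2.2.1 and protocol 8.3.1 collect AEs from consent, about six weeks before dosing (two weeks of screening plus four of run-in), so 5 March could be the true date. What remains is that the SAP has already chosen how to settle such doubt: "if possibly on-treatment, then on-treatment is assumed". In the example both dates are possible, and the rule picks the one that the principle rejects.

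Could the general sentence simply override the bullet? Nothing in either document says so, and a programmer will code the explicit bullet.

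**Conclusion.** The point holds as a minor internal contradiction. Where the month-only rule applies, it can leave a possibly on-treatment AE out of the summary tables, opposite to the direction the SAP says it takes.

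The 41% to 42% is conditional: it describes AEs that were truly on treatment and have only the month missing. It rests on evenly spread first-dose dates and onset days, full 28-day treatment and a known year and end date. It is not a share of all AEs, and reading it that way would turn a rare coding case into a large one. Ignoring the recorded year would raise the 28-day figure to 12 × 378 / 10,220 = 44.4%, but the rule conditions on that year. No efficacy result is touched.

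**What to change.** Replace the month-only bullet in SAP 4.17.1 with:

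> If only the month is missing, impute the earliest month that, with the known day and year, gives a valid calendar date on or after first dose, no later than end of treatment + 96 hours and not after the AE end date. If no such month exists, apply the existing rule, using the earliest month that gives a valid date if the imputed date does not exist.

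The upper bound matters. Without it, first dose on 20 April with day 31 would be imputed to 31 May (Day 42), although the table window closes on 21 May (last dose 17 May + 4 days). The last clause covers impossible dates such as 31 April. Onsets that can only lie in follow-up stay with the existing rule.

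The cost is one bullet of text and a small change to the date-imputation code, with no new data. Under SAP section 1 it goes into a new SAP version before database lock; after lock it needs a SAP addendum and discussion in the CSR. A query for AEs with only the month missing would show whether any record is affected.

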4.17.2 Clinical Laboratory Evaluation

Refer to Section 3.2.2.2 for the list of clinical safety laboratory tests to be performed and the SoA (Table 2 and Table 3), for timing and frequency.

Laboratory values and immune biomarkers measurements including IFNg, IL-10, IL-12p70, IL-13, IL-1b, IL-2, IL-4, IL-6, IL-8, TNFa, CRP, and IgE will be listed by subject and study time point including when possible changes from baseline. In case the units and the normal reference ranges are not the same for all subjects and assessments, units will be standardised to the same units and normalised to the same reference ranges.

The reference ranges and the values outside the clinical reference ranges will be presented and flagged in the data listings. The abnormal values will be flagged with 'L' for values below the lower limit of the clinical reference range and 'H' for values above the upper limit of the clinical reference range and included in the listings. The Investigator will assess whether the values outside the clinical reference range are clinically significant. Clinically significant laboratory values will be recorded by the investigator as AEs.

Statistical Analysis Plan

Descriptive statistics (for clinical chemistry, haematology coagulation parameters and immune biomarkers) will be presented separately for each part by treatment and time for both absolute values (N, mean, SD, median, minimum, maximum) and changes from baseline.

The following figures will be produced:

- Subject profile of haematology laboratory data (absolute values) for Part 1 and mean plots for Part 2.
- Subject profile of clinical chemistry laboratory data (absolute values) for Part 1 and mean plots for Part 2.
- Subject profile of immune biomarkers (absolute values) for Part 1 and Part 2
- Subject profile of CRP, absolute values and mean plots for Part 1 and Part 2.
- Mean immune biomarkers parameters by day, absolute values for Part 1 and Part 2.

Values of the form “ $< x$ ” (ie, below the LLOQ) or “ $> x$ ” (ie, above the upper limit of quantification [ULOQ]) will be imputed as “ x ” in the calculation of summary statistics but displayed as “ $< x$ ” or “ $> x$ ” in the listings.

Shift from baseline to maximum and to minimum on-treatment tables will be presented for laboratory parameters (chemistry, haematology and coagulation, urinalysis and immune biomarkers) including all blood white cells. The number of subjects with treatment emergent haematology abnormalities will be summarised.

The criteria for the haematology treatment emergent abnormalities (respect to baseline) are:

- Confirmed leucocyte count $< 2.0 \times 10^9/L$
- Confirmed neutrophil count $< 1.0 \times 10^9/L$
- Confirmed platelet count $< 75 \times 10^9/L$
- Confirmed lymphocyte count $< 0.5 \times 10^9/L$

Shift tables for the immune biomarkers IFNg, IL-10, IL-12p70, IL-13, IL-1b, IL-2, IL-4, IL-6, IL-8, TNFa, CRP, and IgE, will be presented by treatment and separately for each part.

Individual subject data where alanine aminotransferase/transaminase (ALT) and/or aspartate aminotransferase/transaminase (AST) and total bilirubin are elevated at any time will be listed (ie, ALT and/or AST $\geq 3 \times$ the upper limit of normal [ULN] and total bilirubin $\geq 2 \times$ ULN, at any time) to evaluate potential Hy's Law cases.

A figure for both ALT and AST versus total bilirubin expressed as multiple of ULN will be presented. Plot will be produced on the log scale, and reference lines will be included at $2 \times$ ULN for total bilirubin and at $3 \times$ ULN for ALT/AST.

Clinical laboratory data will be reported in the units provided by the clinical laboratory for the SRC meeting (if applicable), and in System International units in the CSR.

The number and percentage of subjects with a change from baseline in hsCRP higher than 5 and 10 mg/dL will be also reported by specified ADA status.

Figure for hsCRP over time by ADA status and by treatment group will be presented.

Statistical Analysis Plan

On-treatment and treatment emergent definition refer all the assessments with an onset date and time on or after the date and time of first dose of IP up to the end of treatment + 96 hours.

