26 C-reactive protein < 5 mg/L on Day -1.

5.1.4 Part 2-specific Randomisation Criteria at Visit 3

27 Pre-bronchodilator FEV₁ of 40% to 85% (inclusive) predicted.

Prior to spirometry, the following medication withhold periods should be observed:

- (a) SABA and SAMA for at least 6 hours.
- (b) Twice daily LABA and/or LAMA-containing therapies for at least 12 hours.
- (c) Once daily LABA and/or LAMA-containing therapies for at least 24 hours.
- (d) LTRA for at least 24 hours.
- (e) Twice daily theophyllines for at least 12 hours.
- (f) Once daily theophyllines for at least 24 hours.

28 Asthma Control Questionnaire 6 score of ≥ 1.5 .

29 At least 70% compliance with usual asthma controller ICS-LABA during Run-in Period from (Visit 2 to Visit 3) based on daily e-Diary.

30 Minimum 70% compliance with ePRO completion. 70% compliance is defined as completing daily e-Diary for any 7 mornings and any 7 evenings of the last 10 days of the Run-in Period.

31 C-reactive protein < 10 mg/L at Visit 2.

32 A FeNO of ≥ 25 ppb.

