7.1.2.2 Dosing Suspension for Individual Participants (Part 1 and 2)

- Any severe AE or AESI (See Section 8.3.5) with the potential for being classed as a hypersensitivity-like event and not rapidly diagnosed as an infection should result in the suspension of dosing
 - Suspend dosing and fully characterise the event(s).
 - Dosing may resume only in the event of a hypersensitivity-like event being excluded following a full evaluation, including a CRP < 10 mg/L and resolution of the AE(s).

Refer to Section 7.1.1 for further information on FEV₁ 30% decline home assessments to inform dosing suspension as per Investigator discretion.

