Final 5.0	Last Signature	SAP updated for anticipated closure to remove some of the exploratory endpoints, the Per Protocol analysis and subgroup analysis. In addition the AE tables were presented for all the AEs after IP and by ADA status. The table including the number and percentage of subjects with a change from baseline in hsCRP higher than 5 and 10 mg/dL by ADA category and the Figure for hsCRP by week by ADA status and by treatment group will be also presented.

LIST OF ABBREVIATIONS

Abbreviation/Acronym	Definition/Expansion
ACQ-6	Asthma Control Questionnaire-6
ADA	Anti-drug antibody
AE	Adverse event
AESI	Adverse event of special interest
ALT	Alanine aminotransferase/transaminase
ANCOVA	Analysis of covariance
AST	Aspartate aminotransferase/transaminase
ATC	Anatomical therapeutic chemical
AUClast	Area under the serum concentration-curve from zero to the last quantifiable concentration
AUC τ	Area under serum concentration-time curve in the dosing interval
BDRM	Blind data review meeting
BID	Bis in die (twice daily)
BLQ	Below the lower limit of quantification
BMI	Body Mass Index
BP	Blood pressure
CI	Confidence interval
CL/F	Apparent total body clearance of drug from serum after extravascular administration
CRF	Case Report Form
CRP	C-reactive protein
CSP	Clinical study protocol
CSR	Clinical study report
Cmax	Maximum observed (peak) serum concentration
CS	Clinically significant
Ctrough	Concentration immediately prior to dosing
CV	Coefficient of variation
DBP	Diastolic blood pressure

Abbreviation/Acronym	Definition/Expansion
DPI	Dry powder inhaler
DRM	Data Review Meeting
DSMB	Data Safety Monitoring Board
ECG	Electrocardiogram
eCRF	electronic Case Report Form
EN	Enrolled analysis set
FAS	Full analysis set
FDA	Food and Drug Administration
FeNO	Fractional exhaled nitric oxide
FEV ₁	Forced expiratory volume in 1 second
FSH	Follicle stimulating hormone
FVC	Forced vital capacity
GeoCV	Geometric coefficient of variation
GeoLSMeans	Geometric LS means
gSD	Geometric SD
CCI	CCI
HR	Heart rate
ICF	Informed consent form
ICH	International Council for Harmonisation
ICS	Inhaled corticosteroids
IgE	Immunoglobulin E
IL	Interleukin
IP	Investigational Product
IPD	Important protocol deviations
IS	Immunogenicity set
LABA	Long-acting beta-adrenoceptor agonists
LLOQ	Lower limit of quantification
LOCF	Last observation carried forward
MedDRA	Medical Dictionary for Regulatory Activities

Abbreviation/Acronym	Definition/Expansion
MMRM	Mixed model repeated measure
NA	Not applicable

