3.2.2.1 Adverse Events/Serious Adverse Events

Adverse events, including serious AEs (SAEs) will be collected from the time the subject signs the Informed Consent Form (ICF), throughout the Run-in, Treatment Period, and Follow-up Period for any study phase. All AEs will be coded using the most recent version of the Medical Dictionary for Regulatory Activities (MedDRA).

The following variables will be collected for each AE:

- AE diagnosis/description (verbatim)
- The date and time when the AE started and stopped
- Maximum intensity
- Whether the AE is serious or not
- Investigator causality rating against the study intervention (yes or no)
- Action taken with regard to investigational product (IP)
- AE caused participant's withdrawal from the study (yes or no)
- Outcome

Additional variables will be collected for all SAEs including treatment given for the event:

- Date AE met criteria for SAE
- Date investigator became aware of SAE
- AE is serious due to (ie, seriousness criteria)
- Probable cause of death
- Date of death
- Required in-patient hospitalisation or prolongation of existing hospitalisation
- Date of hospitalisation/discharge
- Autopsy performed
- SAE caused by other medication or study procedure

The following intensity ratings will be used:

1. mild (awareness of sign or symptom, but easily tolerated)
2. moderate (discomfort sufficient to cause interference with normal activities)
3. severe (incapacitating, with inability to perform normal activities)

Some AEs are considered of special interest (AESI).

Additionally, C-reactive protein (CRP) ≥ 10 mg/L should be used to support the evaluation and identification of the potential cause of an AESI and to guide further dosing.

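### The table of hsCRP rises by ADA status uses cut-offs of 5 and 10 mg/dL, ten times the mg/L scale used for every other operative CRP value, very probably a unit error

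*SAP*

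**What the plan says.** SAP 4.17.2 (Clinical Laboratory Evaluation) plans a count and percentage of "subjects with a change from baseline in hsCRP higher than 5 and 10 mg/dL will be also reported by specified ADA status". The revision history entry for Final 5.0, the version that added the table, describes it with the same unit: "a change from baseline in hsCRP higher than 5 and 10 mg/dL by ADA category". Section 4.17.2 also states that laboratory data are reported in the laboratory's units for the Safety Review Committee "and in System International units in the CSR".

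The only other CRP output split by ADA status is graphical: "Figure for hsCRP over time by ADA status and by treatment group will be presented". CRP descriptive statistics and shift tables in 4.17.2 are specified by treatment and part, and SAP 4.16 (Immunogenicity Evaluation) has no CRP output.

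Elsewhere the scale is mg/L. Randomisation requires "C-reactive protein < 5 mg/L on Day -1" in Part 1 (Protocol 5.1.3) and "C-reactive protein < 10 mg/L at Visit 2" in Part 2 (Protocol 5.1.4). SAP 3.2.2.1, like Protocol 8.3.5, says that "C-reactive protein (CRP) ≥ 10 mg/L should be used to support the evaluation and identification of the potential cause of an AESI".

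**The concern.** The numerals 5 and 10 are those of the randomisation and dosing limits, but the unit makes them ten times larger. Neither document explains why a rise of 50 or 100 mg/L should be the level of interest when 10 mg/L is the level the trial acts on.

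The effect of immunogenicity on safety is a secondary objective in both parts (SAP 2.1.2 and 2.2.2). The protocol names hypersensitivity-like events as a risk (2.3.1) and uses CRP when excluding them before dosing resumes (7.1.2.2). A table meant to relate ADA status to CRP should register rises on that scale. With the written cut-offs, few or no counts in any ADA group could be taken as evidence of no relation, when moderate rises were simply not counted.

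**Working it through.** There is no derived figure to reproduce. The check is a unit conversion and a comparison of sections.

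**Conversion.** 1 mg/dL = 10 mg/L, so 5 mg/dL = 50 mg/L and 10 mg/dL = 100 mg/L.

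**CRP values elsewhere**

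| Use | Value | Place |
|---|---|---|
| Baseline CRP and hsCRP tables | unit mg/L | SAP 4.6 |
| Part 1 randomisation | below 5 mg/L | Protocol 5.1.3 |
| Part 2 randomisation | below 10 mg/L | Protocol 5.1.4 |
| Part 1 suspension, with a moderate AESI | 10 mg/L or more | Protocol 7.1.2.1 |
| Resuming dosing, both parts | below 10 mg/L | Protocol 7.1.2.2 |
| AESI evaluation | 10 mg/L or more | Protocol 8.3.5, SAP 3.2.2.1 |
| hsCRP rise by ADA status | above 5 and 10 mg/dL = 50 and 100 mg/L | SAP 4.17.2 |

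The mg/L scale is not peculiar to local CRP testing. The Part 2 limit applies at Visit 2, where the schedule lists hs-CRP but no biochemistry sample, and local CRP starts at Visit 3.

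**Value needed to be counted.** Post-baseline value = baseline + cut-off. Assume that baseline still lies within the randomisation limit (0 to 5 mg/L in Part 1, 0 to 10 mg/L in Part 2).

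| Cut-off | Part 1 value above | Part 2 value above |
|---|---|---|
| 5 mg/dL as written | 50 to 55 mg/L | 50 to 60 mg/L |
| 10 mg/dL as written | 100 to 105 mg/L | 100 to 110 mg/L |
| 5 mg/L | 5 to 10 mg/L | 5 to 15 mg/L |
| 10 mg/L | 10 to 15 mg/L | 10 to 20 mg/L |

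Example: 2 to 30 mg/L is a rise of 30 − 2 = 28 mg/L = 2.8 mg/dL. It exceeds both cut-offs in mg/L and neither in mg/dL.

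**Illustration only.** The documents give no hsCRP distribution. Assume a log-normal baseline with median 2 mg/L and CV 100 to 200%, truncated at the randomisation limit; a true fivefold rise; within-participant CV 50 to 100%; and one on-treatment value per participant. By simulation, the percentage of participants above each rise is:

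| Rise above | Limit 5 mg/L (Part 1) | Limit 10 mg/L (Part 2) |
|---|---|---|
| 5 mg/L | 49 to 61% | 55 to 66% |
| 10 mg/L | 27 to 36% | 36 to 41% |
| 50 mg/L | 0.3 to 3.5% | 1.9 to 6.6% |
| 100 mg/L | 0 to 0.6% | 0.1 to 1.8% |

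Section 4.17.2 names no visit for the count. If it means ever exceeding the cut-off, with visits taken as independent, the share above 50 mg/L becomes about 3 to 25% over ten Part 1 visits and 5 to 16% over three Part 2 visits.

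**The case against.** The strongest reply is that the table is descriptive and the data stay visible. Listings, subject profiles and by-treatment tables show the values, AEs are tabulated by ADA status (SAP 4.17.1), and the hsCRP figure is split by ADA status and treatment. All of this stands and limits the importance of the point. None of it supplies a count of rises by ADA status on the scale that the trial uses.

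A second reply is that the unit rules in 4.17.2 settle the matter. They do not: standardising the data and reporting in SI units would turn the cut-offs into 50 and 100 mg/L, not into 5 and 10.

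A third is that the 10 mg/L AESI and dosing limits are absolute levels, whereas the table counts changes. This is correct, so the limits do not dictate the cut-offs for a change. They do show the scale on which CRP is judged, and baselines are expected to be low enough that level and change are of similar size.

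A reader might infer that the table is bound to be nearly empty, or that an ADA effect on CRP would be hidden. The documents do not support that. They give no hsCRP distribution, and the count as written depends on whether one visit or any visit qualifies. A reader might also take the missing plotting statistic for the figure, or the unstated table layout, as further faults. SAP 4.2 leaves remaining presentation detail to the TFL shells, and SAP 4.2 and 4.17 already set the treatment grouping and the denominator.

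**Conclusion.** The point holds as a unit problem in an operative threshold. The tenfold discrepancy is arithmetic and needs no assumption. That it is an error rather than a choice is an inference from the matching numerals, the mg/L baseline table for the same assay and the absence of any rationale. It is very probable, but the documents do not say so, and the repetition in the revision history means that the sponsor should confirm it.

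As written, rises above 5 and up to 50 mg/L are missing from the only numeric CRP-by-ADA summary. If mg/L data are used unconverted, the counts are sensible and the label is ten times too high. The simulated percentages illustrate the direction under assumed distributions and are not a forecast.

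The importance is low. One descriptive table serving a secondary objective is affected. No hypothesis test, primary analysis, AESI definition or individual dosing decision depends on it.

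**What to change.** In SAP 4.17.2, replace mg/dL by mg/L for the hsCRP cut-offs, and make the same change in the Final 5.0 entry of the revision history. If rises of 50 and 100 mg/L are intended, write them in mg/L, give the reason, and add rows for 5 and 10 mg/L.

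The cost is a unit correction using data already collected, with no added test. The lower cut-offs will also pick up intercurrent infections, on placebo as well as on active treatment. The by-treatment presentation already required for safety summaries lets a reader see that.
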